### **Assessments**

Participants will be interviewer-administered baseline, post-test, and 7-month f/u assessments by the Research Assistant since the Clinical Psychologist will be delivering the intervention. Baseline measures will include (those with an \* will also be administered at post-test and 7-month f/u): demographics (e.g., age, income, etc.), tobacco history (e.g., # cigarettes per day, previous attempts, etc.), nicotine dependence\* (Fagerstrom Test for Nicotine Dependence), smoking self-efficacy\* (Smoking Self-Efficacy Scale), depressive symptoms\* (CES-D), and social support.\* These measures have been translated into Portuguese. Exhaled CO levels will be recorded at baseline, post-test, and 7-month f/u. Salivary cotinine will only be assessed at 7-month follow-up.

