### **Sample Size and Statistical Analysis**

As this is a feasibility study, sample size is justified based on the measurement precision of parameters referable for larger study. We are estimating sample size based on the results of the meta-analysis of tobacco cessation among PLWH conducted by Pool et al. where cessation was 13% in the intervention group. For the second phase of feasibility testing with 32 participants, we will be 90% confident that true rate of 7-day point prevalence abstinence at 6-months will be between 3.2% and 22.8%. For 90% confidence interval of true mean, we will be able to estimate 0.3 standard deviation as margin of error with sample size of 32. With conservative consideration of 8% attrition rate over 6 months, the study will recruit 40 participants. Descriptive statistics will be presented for participants' characteristics at each time of measures.

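### Four scales and exhaled CO are repeated on the same people, but no within-person change or interval is planned, and visit summaries may rest on different people

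*Combined protocol and SAP*

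**What the plan says.** The Assessments section lists four scales (nicotine dependence, smoking self-efficacy, depressive symptoms, social support) that are taken at baseline and "will also be administered at post-test and 7-month f/u". It adds that "Exhaled CO levels will be recorded at baseline, post-test, and 7-month f/u". Five measures are therefore taken three times on the same people. Salivary cotinine is taken once, at 7 months, and is not part of this point.

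The analysis plan is the single paragraph under Sample Size and Statistical Analysis. It justifies the sample size by how precisely quantities useful to a larger study can be measured. It then gives:

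- an expected 90% interval of 3.2% to 22.8% for the abstinence rate at n = 32;
- a precision statement for a mean: "we will be able to estimate 0.3 standard deviation as margin of error with sample size of 32";
- an attrition statement: "With conservative consideration of 8% attrition rate over 6 months, the study will recruit 40 participants";
- one sentence on reporting: "Descriptive statistics will be presented for participants' characteristics at each time of measures".

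The documents contain no change score, paired analysis, repeated-measures model, baseline restricted to those followed up, or missing-data rule for the repeated measures.

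**The concern.** Summaries made separately at each visit leave out two things.

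First, they do not give the mean change within a person, the SD of that change or an interval for it, and they do not show the within-person correlation. A team sizing a larger study on any of these measures would want those quantities, and the visit means and SDs alone cannot supply them.

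Secondly, the people summarised at baseline need not be those summarised at 7 months. Anyone who subtracts one visit mean from the other combines true change with change in who is present. If the two sets are also treated as independent, the within-person correlation is ignored and the contrast will usually look less precise than the data allow.

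The stakes are limited to these secondary measures. The primary outcome, seven-day abstinence at 7 months, is a proportion at one time and needs no change score.

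**Working it through.** **Inputs from the plan (Sample Size and Statistical Analysis):** two-sided 90% confidence, abstinence rate 13%, 32 evaluable, 40 recruited, 8% attrition, 0.3 SD margin for a mean.

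**Inputs not in the plan (assumptions):** within-person correlation r, taken from 0.3 to 0.8; equal SDs at both visits; a baseline difference d between those lost and those retained, taken from 0.25 to 1.0 SD.

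**1. The plan's own figures**

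- Abstinence interval: 0.13 ± 1.645 × √(0.13 × 0.87 / 32) = 3.22% to 22.78%. Reproduced.
- Margin for a mean of 32 values: t(0.95, 31 df)/√32 = 0.2997 SD (0.291 SD with the normal quantile). Reproduced as 0.3 SD.
- Recruitment: 32/(1 − 0.08) = 34.8, so 35. The stated 40 is not reproduced. It corresponds to 20% attrition: 32/(1 − 0.20) = 40.

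The loss is therefore either 40 × 0.08 = 3.2, about 3 people (about 37 left), or 40 − 32 = 8 people.

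**2. Precision for within-person change**

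With equal SDs, the SD of change is SD × √(2(1 − r)), so the 90% margin is t × √(2(1 − r)/n), in units of the SD at one visit.

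| r (assumed) | n = 32 | n = 37 |
|---|---|---|
| 0.3 | 0.355 | 0.328 |
| 0.5 | 0.300 | 0.278 |
| 0.7 | 0.232 | 0.215 |
| 0.8 | 0.190 | 0.176 |

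The n = 32 value at r = 0.3 is 0.2997 × √1.4 = 0.3546, which is 0.35 to two decimals.

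**3. Treating visit means as separate samples**

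t(0.95, 70 df) × √(1/40 + 1/32) = 0.395 SD (0.390 SD with the normal quantile).

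The paired margin at n = 32 equals this when 2(1 − r) = (0.395/0.2997)², that is, at r of about 0.13. Above that, pairing is tighter. At r = 0.3 the gain is (0.395 − 0.355)/0.395, about 10%. At r = 0.8 the margin is less than half (0.190 against 0.395).

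**4. Shift from a change in who is present**

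If a fraction f is lost, the baseline mean of everyone minus the baseline mean of those retained is f × d. With no true change, the difference in visit means moves by that amount.

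| d (assumed, SD) | 3 of 40 lost | 8 of 40 lost |
|---|---|---|
| 0.25 | 0.019 | 0.05 |
| 0.5 | 0.038 | 0.10 |
| 1.0 | 0.075 | 0.20 |

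Every entry is below the plan's 0.3 SD margin.

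**The case against.** This is a single-group feasibility study with one stated outcome, and describing secondary scales visit by visit is defensible. The raw data would still allow paired summaries later. The plan does not propose to subtract or test visit means, so any misreading would be the reader's. All of this stands, and it keeps the severity low. It does not fill the gap: change, its SD and their precision are still unplanned in a study justified by precision for a larger one.

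Five stronger readings are tempting, and the documents do not support them.

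- **That the plan expects to lose 8 of 40.** Eight follows only from 40 minus 32. The stated 8% gives about 3. The plan contradicts itself, and neither figure can be called its expectation.
- **That visit means are biased by attrition.** They can be, if those lost differ at baseline. No document gives that difference, and the assumed range yields shifts smaller than the plan's own margin.
- **That the 0.3 SD margin is for one visit and so excludes change.** The text does not say which mean is meant. The value 0.2997 holds for any mean of 32 values, including a mean change expressed in SDs of change. The fair criticism is that the mean is unspecified.
- **That the repeat measurements were scheduled to show change.** The Assessments section gives no objective for them, so that purpose would be an inference.
- **That descriptive summaries are the only inference planned.** Precision statements for the abstinence rate and for a mean are also given, although neither concerns change in a named measure.

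The precision gain is also conditional. It needs an assumed r and equal SDs, and equal SDs are doubtful for CO in a programme where some participants stop smoking. The 40 and 32 are the sample-size section's figures. The Feasibility Testing – Research Protocol section also has 10 pilot participants, and if no changes are needed the 40 are enrolled within Phase II, so the actual denominators may differ.

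**Conclusion.** The point holds in a limited form. Five measures are repeated on the same people and the plan commits to no estimate of within-person change. That gap does not depend on the attrition rate.

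With 32 pairs, the 90% margin for change would be 0.19 to 0.35 SD for r from 0.8 to 0.3, given equal SDs at both visits, against about 0.40 SD if 40 and 32 values are treated as separate samples. The possible shift from a change in who is present is modest: about 0.04 SD (3 lost) or 0.10 SD (8 lost) at an assumed baseline difference of 0.5 SD, and at most 0.20 SD over the range examined. The conflict between 8% attrition and 40 recruited for 32 evaluable is a separate inconsistency that must be resolved.

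Severity is low. A reader might infer that the main result is compromised. It is not, because abstinence at 7 months is a single-time proportion and does not rely on these summaries.

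**What to change.** Extend the final sentence of Sample Size and Statistical Analysis along these lines:

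> For each scale and for exhaled CO, the mean within-person change from baseline to post-test and from baseline to 7 months will be reported with its SD and a 90% confidence interval, in participants with both values. Baseline values will be shown separately for participants retained and participants lost.

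In addition:

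- State which mean the 0.3 SD margin refers to, and give the expected margin for change over a range of r (0.19 to 0.35 SD for r = 0.8 to 0.3 at n = 32), noting the equal-SD assumption.
- Reconcile 8% attrition with 40 recruited and 32 evaluable, and restate the margins if the evaluable number changes.
- A repeated-measures mixed model may be added as support, but is optional at this size.

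Paired change removes the mismatch in who is compared. It does not remove bias if those lost would have changed differently, which is why the baseline comparison of retained and lost participants should accompany it.

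The cost is wording and a small amount of analysis: no new data, visits or participants.
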